2.2 PARTICIPANT REGISTRATION AND STATUS UPDATE PROCEDURES

Registration and status updates (e.g., when a participant is taken off protocol therapy and when a participant is taken off-study) will take place per CCR SOP ADCR-2, CCR Participant Registration & Status Updates found at:

<https://ccrod.cancer.gov/confluence/pages/viewpage.action?pageId=73203825>.

2.2.1 Treatment Assignment Procedures

Cohorts

Number	Name	Description
1	Cohort 1	Men with Prostate Cancer

Arms

Number	Name	Description
1	Lead-in CRPC Cohort	PROSTVAC-V on week 0 followed by booster injection called PROSTVAC-F on 2, 4, and 8 weeks. Nivolumab will be administered every 2 weeks, starting at week 2. When administered on the same day, the preferred order of administration is PROSTVAC first followed by nivolumab. Participants will undergo restaging scans on week 12 prior to receiving treatment. If no PD, option to continue treatment with nivolumab every 2 weeks and PROSTVAC-F every 4 weeks until intolerance or progression (evaluated radiographically every 12 weeks). Participants who remain on protocol beyond 1 year will have the option of extending the nivolumab dosing interval to every 4 weeks.
2	Neoadjuvant Cohort	PROSTVAC-V on week 0 followed by booster injection called PROSTVAC-F on 2, 4 and 8 weeks. Nivolumab will be administered on weeks 2, 4, 6, and 8. When administered on the same day, the preferred order of administration is PROSTVAC first followed by nivolumab. Participants will undergo prostatectomy on week 9. (If surgery is scheduled earlier than 9 weeks after initial dosing, the 6 and 8 week dosing may be skipped and surgery may be done as early as week 5.)

Arm Assignment

Participants in cohort 1 will be assigned to arm 1 until the expected number of participants enrolled (n=10), then participants will be assigned to arm 2 (n=17).

2.3 BASELINE EVALUATION

2.3.1 For Lead-In CRPC Cohort

To be performed within 16 days prior to initiation of study therapy (these tests will not need to be repeated if they were done at screening within the appropriate timeframe):

- History and physical exam including weight and vital signs
- ECOG performance status
- CBC with differential and platelet count, prothrombin time/INR, activated partial thromboplastin time
- HLA class 1 profile (May be obtained any time prior to enrollment)
- Urinalysis (may be omitted in participants with incontinence who cannot produce a clean sample)
- Serum chemistries (Na⁺, K⁺, Cl⁻, CO₂, BUN, creatinine, glucose, AST/ALT, bilirubin, calcium, phosphorous, albumin, magnesium, alkaline phosphatase, LDH, ionized calcium, amylase, lipase, total protein, uric acid)
- Serum Testosterone level
- Serum PSA
- CPK
- Lymphocyte Phenotyping (TBNK)
- Baseline electrocardiogram 12 lead ECG (EKG) on all participants, and appropriate cardiologic evaluation, as clinically indicated, to provide baseline function and identify any participants who should be monitored closely for cardiac risks associated with vaccinia vaccination
- Immunology assays (including immune T-cell response assay, CD3, 4, 8 subsets and CD4:CD8 ratio, Class II immune responses, CTL assay, and sera antibody analyses)
- Biopsy (May be obtained any time after enrollment and prior to treatment initiation; optional)
- Scans (CT CAP and bone scan)

2.3.2 For neoadjuvant cohort

To be performed within 16 days prior to enrollment unless specifically stated otherwise (these tests will not need to be repeated if they were done at screening within the appropriate timeframe):

- Baseline examinations need not be repeated if they have been performed within the appropriate time frame.
- History and Physical Exam
- ECOG Performance Status
- HLA class 1 profile (May be obtained any time prior to enrollment)
- Serum PSA (tumor marker)
- CBC
- Urinalysis (may be omitted in participants with incontinence who cannot produce a clean sample)
- Serum chemistries (Na+, K+, Cl-, CO2, BUN, creatinine, glucose, AST/ALT, bilirubin, calcium, phosphorous, albumin, magnesium, alkaline phosphatase, LDH, ionized calcium, amylase, lipase, total protein, uric acid, C-reactive protein)
- Lymphocyte Phenotyping (TBNK)
- Baseline electrocardiogram 12 lead ECG (EKG) on all participants, and appropriate cardiologic evaluation, as clinically indicated, to provide baseline function and identify any participants who should be monitored closely for cardiac risks associated with vaccinia vaccination
- Research Studies (See Section 5 for details)
- MRI prostate (can be obtained within one year prior to treatment) MRI of the prostate will be performed prior to and after vaccination course if logistically feasible.
- Immunology assays (including immune T-cell response assay, CD3, 4, 8 subsets and CD4:CD8 ratio, Class II immune responses, CTL assay, and sera antibody analyses)
- Prostate biopsy (performed only if previously collected tissue is not available. If biopsy was performed at screening, leftover material may be used for research study.)

3 STUDY IMPLEMENTATION

3.1 STUDY DESIGN

3.1.1 Rationale for Serial Cohort Design

The primary focus of this study will be to evaluate PROSTVAC and nivolumab in the neoadjuvant setting. However, given the concern that treating with these agents prior to radical prostatectomy may delay or compromise definitive radical prostatectomy (due to systemic adverse events or local inflammation) we will have a lead-in cohort evaluating the safety and tolerability of this combination in the castration resistant setting.

Participants in this initial cohort will be enrolled not more than 3 a week.

Following this lead-in cohort in the CRPC setting, we propose a cohort in the neoadjuvant setting evaluating the combination of PROSTVAC and nivolumab.

Abbreviated Title: Prostvac-Nivo in prostate ca

Version Date: 01.10.2023

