3.4 STOPPING RULES

The study may be halted if any of the following safety conditions are met:

Abbreviated Title: Prostvac-Nivo in prostate ca

Version Date: 01.10.2023

- If one or more deaths occur, we will immediately stop accrual and we will promptly discuss this with the NIH Intramural IRB and the FDA. In addition, the study will be halted if any death occurs within 30 days of treatment regimen.
- If two or more participants develop a Grade 4 toxicity at any point in the study attributable to the treatment regimen that does not resolve to Grade 2 within 10 days.

Abbreviated Title: Prostvac-Nivo in prostate ca
Version Date: 01.10.2023

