10 STATISTICAL CONSIDERATIONS

For the initial lead-in cohort, the primary objective is safety, especially detection of clinically important inflammation defined as a grade 3 diarrhea or colitis requiring steroids or anti cytokine therapy or not resolving to grade 1 or less within 28 days. If there are 10 participants evaluated in the lead-in cohort and if 0/10 have clinically important inflammation, then this will be considered acceptable for proceeding with the neoadjuvant cohort. On the other hand, if 1/10 or more have significant inflammation, then we will discuss with the IRB, FDA and sponsor amending the trial, since the upper one-sided 90% confidence interval on 1/10 is 33.7% which would be consistent with an excessive rate of inflammation.

After the lead-in cohort, participants on this study will be assigned to PROSTVAC and Nivolumab (neoadjuvant cohort) for 9 weeks. Utilizing computer automated staining analysis, density of cell infiltrate will be calculated and the pre- and post-treatment values will be compared to determine response to treatment. All measurement will be determined in a blinded fashion with respect to the treatment groups. The primary evaluation will be of a comparison of differences between the neoadjuvant cohort and participants treated on the 14-C-0112 protocol (NCT02153918), of the changes of the CD3 + T cells, measured from baseline to the radical prostatectomy at 9 weeks on the present trial, and from baseline to the radical prostatectomy at 12 weeks in participants treated on the 14-C-0112 trial.

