Slides made from prostate biopsy specimens (collected at baseline) and prostatectomy specimens (collected at surgery performed after last dose of vaccine) will be stained for CD4 and CD8 cells and digitized for analysis of immune cell infiltrate. Other markers such as CD4/FoxP3 may also be stained for further correlative studies. These studies will be performed by the Laboratory of Tumor Immunology and Biology. At a minimum, 5 slides from one biopsy core confirmed to contain cancer will be needed for baseline quantification. Attempts will be made based on anatomic location notation or when available, MRI based location, to correlate biopsy location with pathologic location on prostatectomy specimens. When feasible, quantitation will be performed in triplicate. Quantitation will be reported as number of stained cells per micron squared of surface area. Wilcoxon matched pair signed rank test, Friedman test with Dunn's multiple comparisons, or alternative statistical models will be used as appropriate. Aperio ScanScope digital scanner systems with Aperio ImageScope software algorithms will be used. Manual quantitation will be performed in case of software malfunction. Isotype antibodies negative controls will be included in all runs. Tonsil or lymph node tissue will be positive control for CD4 and CD8. Slides will be developed with primary and secondary antibodies per manufacturer specifications for visualization of cells.

The lead-in safety cohort will require 10 participants and the neoadjuvant cohort will require 17 evaluable participants. In order to allow for a small number of inevaluable participants, the accrual ceiling will be set to 29 participants. If 3-4 participants per month enroll onto this study, accrual is expected to be completed in one year.

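### The lead-in fails at its first qualifying event, but no written rule makes the review act then, so enrolment may run on towards 10

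*Combined protocol and SAP*

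**What the plan says.** Section 10 defines the lead-in event: "clinically important inflammation defined as a grade 3 diarrhea or colitis requiring steroids or anti cytokine therapy". A second limb of the definition covers such an event when it is still above grade 1 after 28 days. The pass condition is that "if 0/10 have clinically important inflammation, then this will be considered acceptable for proceeding with the neoadjuvant cohort". The fail condition is that "if 1/10 or more have significant inflammation, then we will discuss with the IRB, FDA and sponsor amending the trial". The stated reason is that "the upper one-sided 90% confidence interval on 1/10 is 33.7" percent. Both outcomes are introduced by reference to 10 participants evaluated, and no pause in enrolment is mentioned.

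Section 2.2.1 (Arm Assignment) assigns participants to the lead-in arm until 10 are enrolled and then to the neoadjuvant arm, with no check in between.

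Section 3.1.1 sets the pace: "Participants in this initial cohort will be enrolled not more than 3 a week". Section 10 expects much slower accrual: "If 3-4 participants per month enroll onto this study, accrual is expected to be completed in one year".

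Section 3.4 acts throughout the study, on any death or on this condition: "If two or more participants develop a Grade 4 toxicity at any point in the study attributable to the treatment regimen", where the toxicity has not resolved to grade 2 within 10 days.

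Three further provisions bear on the point. The team meets about weekly to discuss each participant (Section 7.5.1). Serious events go to the sponsor's safety office within 24 hours (Section 8.3). The study may be suspended for unacceptable risk (Section 13.1). None of the three names this event.

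**The concern.** The criterion tolerates no events, so it can fail well before 10 participants have been evaluated. From then on, further lead-in enrolment cannot change the written decision, which is the same for one event as for several. The plan does not say whether the discussion with the IRB, FDA and sponsor starts at that moment or once the cohort is complete. Followed literally, Sections 2.2.1 and 10 allow new participants to start the combination after the trial's own condition has failed. The event Section 10 singles out as the main safety interest of the lead-in would then depend on judgement, although a numerical rule for it already exists.

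**Working it through.** **1. The plan's own figure.** The exact one-sided 90% upper bound for 1/10 solves (1-p)^10 + 10p(1-p)^9 = 0.10, which gives p = 33.68%. The stated 33.7% is reproduced.

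**2. How often the criterion fails.** P(at least one event in 10) = 1-(1-p)^10. This is 40% at a true rate of 5%, 65% at 10%, 89% at 20% and 98% at 33.7%.

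**3. Does Section 3.4 catch the event?** One grade 3 diarrhea or colitis is neither a death nor two unresolved grade 4 toxicities, so it does not.

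**4. Accrual.** One month is 365.25/7/12 = 4.348 weeks.

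- Planned: 3/4.348 = 0.69 to 4/4.348 = 0.92 a week, so 10 participants take 10/0.92 = 10.9 to 10/0.69 = 14.5 weeks.
- Cap: 3 × 4.348 = 13.0 a month, which is 13.0/4 = 3.3 to 13.0/3 = 4.3 times the plan. Cumulative starts are 3, 6, 9 and 10 at weeks 0, 1, 2 and 3.

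This applies the whole-study accrual rate to the lead-in, which is an assumption.

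**5. How many are still unenrolled when the first event is known?** The documents give no lag from a participant's week 0 to a known event. Nivolumab starts at week 2, and one limb of the event definition can take up to 28 days, so lags L of 4, 6 and 8 weeks are assumed. With evenly spaced enrolment at r a week, floor(rL) further participants have enrolled by the time an event is known. Put N = 10 - floor(rL). Given at least one event, the mean number not yet enrolled is

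[N - (1-(1-p)^N)/p] / [1-(1-p)^10].

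Example at 3 a month, L = 4, p = 0.10: rL = 2.76, so N = 8, and (8 - 5.695)/0.6513 = 3.5.

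| Accrual | Lag (weeks) | N | p = 10% | p = 20% | p = 33.7% |
|---|---|---|---|---|---|
| 3 a month | 4 | 8 | 3.5 | 4.3 | 5.2 |
| 3 a month | 6 | 6 | 2.0 | 2.6 | 3.3 |
| 3 a month | 8 | 5 | 1.4 | 1.8 | 2.5 |
| 4 a month | 4 | 7 | 2.7 | 3.4 | 4.3 |
| 4 a month | 6 | 5 | 1.4 | 1.8 | 2.5 |
| 4 a month | 8 | 3 | 0.4 | 0.6 | 0.9 |

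At 3 a week all 10 have started by week 3, so the number is 0 for every lag of 4 weeks or more.

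**The case against.** The strongest reply is that the gate serves another purpose. Section 3.1.1 explains the lead-in by the concern that treatment might delay or compromise prostatectomy, and Section 10 makes 0/10 the condition for opening the neoadjuvant cohort. It is not written as a toxicity boundary for the castration-resistant participants themselves. Failing it does not show that treating them must stop, and a full 10 would separate 1/10 from, say, 4/10, which could inform an amendment. This stands as a reason to count lost precision as a cost. It does not settle when the review should start, because Section 10 states one action for any count of 1 or more and gives no use for completing the cohort after failure.

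A reader might infer several stronger things that the documents do not support:

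- **Enrolment must continue to 10 before anyone acts.** The text does not order this. The condition 1/10 or more is certain at the first event and can be read as acting then, and Sections 7.5.1, 8.3 and 13.1 leave room to intervene.
- **Most of the cohort is avoidably exposed.** The expected number enrolled after the first-event participant is the sum over k of (10-k)p(1-p)^(k-1), or 7.1, 5.5 and 3.5 at 33.7%, 20% and 10%. That assumes each outcome is known before the next participant enrols, which neither the planned pace nor the cap allows.
- **Nine of 10 will have started when nivolumab is first given.** This holds only at the cap, more than three times planned accrual, and cannot be combined with figures based on the planned pace.
- **The weekly cap is itself an error.** It does not bind on average, but a cap can guard against bursts. At one participant every 1.1 to 1.4 weeks (1/0.92 to 1/0.69), planned accrual is already spread out.

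**Conclusion.** The gap is one of timing and is worth closing. The criterion can fail at the first event, the rule is worded on 10 evaluated, the arm fills to 10, and no continuous rule covers that event. Enrolment may continue after failure; the plan does not say that it will.

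Given at least one event, a pause at that point would find on average about 0.4 to 5.2 of the 10 not yet enrolled at planned accrual, and none at 3 a week. The range rests on the assumed 4-8 week lag, evenly spaced enrolment, true rates of 10% to 33.7% and lead-in accrual at the whole-study rate. The existence of the gap depends on none of these. At the permitted maximum pace the pause would come too late to spare anyone, and whether a different stagger is warranted is for the sponsor to decide.

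**What to change.** Reconcile Sections 2.2.1, 3.4 and 10. In Section 10, state that the condition 1/10 or more is met at the first qualifying event, that the IRB, FDA and sponsor discussion is triggered then, and that further lead-in enrolment is paused until it concludes. Cross-refer to this in Section 3.4, and in the arm assignment text of Section 2.2.1, which counts participants enrolled where Section 10 counts participants evaluated. The change concerns enrolment and the timing of review; it says nothing about the treatment of participants already on study.

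The drafting cost is a sentence or two and two cross-references. The operational cost is a possible short pause in lead-in accrual and a less precise event rate if the cohort is not completed. The pause is not free. The text has "the accrual ceiling will be set to 29 participants", and at 3-4 a month these take 29/4 = 7.3 to 29/3 = 9.7 months. That leaves roughly 2.3 to 4.8 months of the planned year, from which any observation period between the cohorts must also come.

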3.1.2 Study Schema

Lead-in CRPC Cohort for safety:

	Week 0	Week 2	Week 4	Week 6	Week 8	Week 10	Week 12
N = 10	PROSTVA C-V	PROSTVA C-F Nivolumab	PROSTVA C-F Nivolumab	Nivolumab	PROSTVA C-F Nivolumab	Nivolumab	Restaging CT and Bone scan and if no PD option to continue treatment until intolerance or progression (evaluated radiographically every 12 weeks)

PROSTVAC-V 2×10^8 Infectious Units

PROSTVAC-F 1×10^9 Infectious Units

Nivolumab 240 mg (Flat dose) every 2 weeks. Alternately, participants who remain on protocol beyond 1 year may transition to nivolumab 480 mg (flat dose) every 4 weeks.

Neoadjuvant Cohort:

	Week 0	Week 2	Week 4	Week 6*	Week 8*	Week 9*
N=17	PROSTVAC-V	PROSTVAC-F Nivolumab	PROSTVAC-F Nivolumab	Nivolumab	PROSTVAC-F Nivolumab	Prostatectomy

PROSTVAC-V 2×10^8 Infectious Units

PROSTVAC-F 1×10^9 Infectious Units

Nivolumab 240 mg (Flat dose)

*If surgery is scheduled earlier than 9 weeks after initial dosing, the 6 and 8 week dosing may be skipped and surgery may be done as early as week 5.

3.2 DRUG ADMINISTRATION

3.2.1 PROSTVAC Vaccine

All vaccines in this trial should be handled according to the guidelines outlined by each department. Study staff administering the vaccine or assessing the vaccine site should wear personal protection consistent with the standard of practice outlined by each department or unit. Participants receiving PROSTVAC-V should be isolated just prior to the administration of

vaccine and can be removed from isolation after the vaccine is administered and bandage is secured over the injection site. Appendix B (Section 16.2) defines individuals at risk for vaccinia exposure.

PROSTVAC-V (vaccinia) will be administered subcutaneously in an extremity (e.g., thigh) at a dose of 2×10^8 infectious units.

PROSTVAC-F (fowlpox) will be administered subcutaneously in an extremity (e.g., thigh) at a dose of 1×10^9 infectious units.

3.2.2 Nivolumab

Nivolumab is to be administered as a flat dose of 240 mg or 480 mg over approximately 30-minutes via IV infusion, using a volumetric pump with a 0.2/1.2 micron in-line filter at the protocol-specified dose. Nivolumab injection can be infused undiluted or diluted so as not to exceed a total infusion volume of 160 mL. Nivolumab may be diluted with 0.9% sodium chloride injection, USP or 5% dextrose injection, USP. It is not to be administered as an IV push or bolus injection. At the end of the infusion, flush the line with a sufficient quantity of normal saline.

3.2.3 PROSTVAC with Nivolumab

Toxicity management for the combined agents follows the same template guidelines and algorithms that are provided in Section 16.3 for single agent nivolumab.

When administered on the same day, the preferred order of administration is PROSTVAC first followed by nivolumab.

3.3 DOSE MODIFICATIONS

Participants must have recovered to \leq grade 1 attributable toxicity for the parameters used to assess levels of organ function required for eligibility (see Section 2.1) after each treatment in order to receive a subsequent treatment. Participants who experience irAE may continue PROSTVAC alone if irAE appears to be driven by nivolumab. In such circumstances, investigator will discuss fully the potential risks with the participant and document that conversation appropriately. Any dosing interruption lasting > 6 weeks from the last dose will require participants to be removed from protocol with the following exceptions:

- Dosing interruptions to allow for prolonged steroid tapers to manage drug-related adverse events are allowed. Tumor imaging assessments should continue as per protocol even if dosing is interrupted
- Dosing interruptions > 6 weeks from the last dose that occur for non-drug-related reasons may be allowed
- For subjects with mCRPC who have stopped receiving nivolumab because of grade 3 or higher irAEs, nivolumab could be re-started if the participant had partial response according Prostate Cancer Working Group 3 (PCWG 3) and RECIST 1.1 criteria but subsequently develops PSA progression (by PCWG 3) while on PROSTVAC alone.

3.4 STOPPING RULES

The study may be halted if any of the following safety conditions are met:

Abbreviated Title: Prostvac-Nivo in prostate ca

Version Date: 01.10.2023

- If one or more deaths occur, we will immediately stop accrual and we will promptly discuss this with the NIH Intramural IRB and the FDA. In addition, the study will be halted if any death occurs within 30 days of treatment regimen.
- If two or more participants develop a Grade 4 toxicity at any point in the study attributable to the treatment regimen that does not resolve to Grade 2 within 10 days.

Abbreviated Title: Prostvac-Nivo in prostate ca
Version Date: 01.10.2023

3.5 STUDY CALENDAR

3.5.1 Lead-in CRPC Cohort

	Screening	Week 0 (Baseline)	Week 2 (+/- 3 days)	Week 4 (+/- 3 days)	Week 6 (+/- 3 days)	Week 8 (+/- 3 days)	Week 10 (+/- 3 days)	Follow-up q 2 weeks until off treatment	Safety Visit 4-5 weeks after treatment discontinuation ⁹
Treatment									
Vaccinia- PROSTVAC		X							
Fowlpox- PROSTVAC			X	X		X		X ⁴	
Nivolumab (Flat dose)			X	X	X	X	X	X ⁴	
Assessments									
History and PE, Weight	X ²	X ³	X	X	X	X	X	X ⁴	X
Height	X ⁵								
ECOG Performance Score	X ²	X ³	X	X	X	X	X	X ⁴	X
ECG		X ³							
HIV/Hep B and C tests	X ⁵								
HLA class I profile		X ³							
Immunology Assays/TBNK	X	X ³							

Abbreviated Title: Prostvac-Nivo in prostate ca
Version Date: 01.10.2023

	Screening	Week 0 (Baseline)	Week 2 (+/- 3 days)	Week 4 (+/- 3 days)	Week 6 (+/- 3 days)	Week 8 (+/- 3 days)	Week 10 (+/- 3 days)	Follow-up q 2 weeks until off treatment	Safety Visit 4-5 weeks after treatment discontinuation ⁹
Pathologic confirmation of dx ¹	X ¹								
Labs (see Sections 2.1.4 and 2.2.1)	X ²	X ³							
Labs: CBC, TSH, amylase, lipase, PSA, PT, PTT and the following panels: acute care, mineral, hepatic			X	X	X	X	X	X	X
Research labs: 6 green tops (PBMCs) and 2 SSTs (serum).		X	X	X			X	X ^{7,8}	X
Prostate biopsy (optional)		X							
Restaging CT and Bone scan ⁴								X ⁸	X
Tc 99 scintigraphy	X ⁶	X							

Abbreviated Title: Prostvac-Nivo in prostate ca
Version Date: 01.10.2023

	Screening	Week 0 (Baseline)	Week 2 (+/- 3 days)	Week 4 (+/- 3 days)	Week 6 (+/- 3 days)	Week 8 (+/- 3 days)	Week 10 (+/- 3 days)	Follow-up q 2 weeks until off treatment	Safety Visit 4-5 weeks after treatment discontinuation ⁹
CT-C/A/P or MRI	X ⁶	X							

¹Pathologic confirmation will be obtained any time prior to enrollment

²Screening assessments obtained within 16 days prior to enrollment

³Baseline assessments obtained within 16 days prior to initiation of study therapy (these tests will not need to be repeated if they were done at screening within the appropriate timeframe)

⁴If no PD option to continue treatment until intolerance or progression (evaluated radiographically using irRC every 12 weeks). PROSTVAC-F is administered every 4 weeks (i.e., weeks 12, 16, 20, etc.) Nivolumab is administered at a flat dose of 240mg every 2 weeks (+/- 3 days). For participants who remain on protocol beyond 1 year, nivolumab 480mg (flat dose) every 4 weeks (+/- 3 days) may be administered instead of the 240 mg every 2-week (+/- 3 days) regimen.

⁵To be obtained within 8 weeks prior to start of enrollment

⁶To be obtained within 4 weeks prior to start of enrollment

⁷Restaging visits only

⁸Per PI discretion. For example, participants who have had a complete response to treatment may have the interval between re-staging imaging increased to 1 year. Research samples for these participants will also be collected yearly with staging.

⁹ Assessment of SAEs at approximately 100 days (\pm 1 week) after nivolumab discontinuation. Assessment may be conducted by phone if the participant cannot come to the NIH. Assessments may also be performed by a local provider.

Abbreviated Title: Prostvac-Nivo in prostate ca
Version Date: 01.10.2023

